6.3.5 Overall survival

Overall survival: Defined as the time from treatment initiation to the time of death.

6.4 TOXICITY CRITERIA

The following adverse event management guidelines are intended to ensure the safety of each patient while on the study. The descriptions and grading scales found in the revised NCI Common Terminology Criteria for Adverse Events (CTCAE) version 5.0 will be utilized for AE reporting. All appropriate treatment areas should have access to a copy of the CTCAE version 5.0. A copy of the CTCAE version 5.0 can be downloaded from the CTEP web site (http://ctep.cancer.gov/protocolDevelopment/electronic_applications/ctc.htm50).

7 NIH REPORTING REQUIREMENTS / DATA AND SAFETY MONITORING PLAN

7.1 DEFINITIONS

Please refer to definitions provided in Policy 801: Reporting Research Events found at: <https://irbo.nih.gov/confluence/pages/viewpage.action?pageId=36241835#Policies&Guidance-800Series-ComplianceandResearchEventReportingRequirements>.

7.2 OHSRP OFFICE OF COMPLIANCE AND TRAINING / IRB REPORTING

7.2.1 Expedited Reporting

Please refer to the reporting requirements in Policy 801: Reporting Research Events and Policy 802 Non-Compliance Human Subjects Research found at:

<https://irbo.nih.gov/confluence/pages/viewpage.action?pageId=36241835#Policies&Guidance-800Series-ComplianceandResearchEventReportingRequirements>. Note: Only IND Safety Reports that meet the definition of an unanticipated problem will need to be reported per these policies.

7.2.2 IRB Requirements for PI Reporting at Continuing Review

Please refer to the reporting requirements in Policy 801: Reporting Research Events found found at:

<https://irbo.nih.gov/confluence/pages/viewpage.action?pageId=36241835#Policies&Guidance-800Series-ComplianceandResearchEventReportingRequirements>.

7.3 NCI CLINICAL DIRECTOR REPORTING

Problems expeditiously reviewed by the OHSRP in the NIH eIRB system will also be reported to the NCI Clinical Director/designee; therefore, a separate submission for these reports is not necessary.

In addition to those reports, all deaths that occur within 30 days after receiving a research intervention should be reported via email unless they are due to progressive disease.

To report these deaths, please send an email describing the circumstances of the death to at [contact] within one business day of learning of the death.

7.4 NIH REQUIRED DATA AND SAFETY MONITORING PLAN

7.4.1 Principal Investigator/Research Team

The clinical research team will meet on a regular basis weekly when patients are being actively treated on the trial to discuss each patient.

All data will be collected in a timely manner and reviewed by the principal investigator or a lead associate investigator. Events meeting requirements for expedited reporting as described in section **7.2.1** will be submitted within the appropriate timelines.

The principal investigator will review adverse event and response data on each patient to ensure safety and data accuracy. The principal investigator will personally conduct or supervise the investigation and provide appropriate delegation of responsibilities to other members of the research staff.

8 SPONSOR PROTOCOL/SAFETY REPORTING

8.1 DEFINITIONS

8.1.1 Adverse Event

Any untoward medical occurrence in a patient or clinical investigation subject administered a pharmaceutical product and which does not necessarily have a causal relationship with this

treatment. An adverse event (AE) can therefore be any unfavorable and unintended sign (including an abnormal laboratory finding), symptom, or disease temporally associated with the use of a medicinal (investigational) product, whether or not related to the medicinal (investigational) product (ICH E6 (R2)).

8.1.2 Serious Adverse Event (SAE)

An adverse event or suspected adverse reaction is considered serious if in the view of the investigator or the sponsor, it results in any of the following:

- Death
- A life-threatening adverse event (see section [8.1.3](#))
- Inpatient hospitalization or prolongation of existing hospitalization
 - A hospitalization/admission that is pre-planned (i.e., elective or scheduled surgery arranged prior to the start of the study), a planned hospitalization for pre-existing condition, or a procedure required by the protocol, without a serious deterioration in health, is not considered a serious adverse event.
 - A hospitalization/admission that is solely driven by non-medical reasons (e.g., hospitalization for patient or subject convenience) is not considered a serious adverse event.
 - Emergency room visits or stays in observation units that do not result in admission to the hospital would not be considered a serious adverse event. The reason for seeking medical care should be evaluated for meeting one of the other serious criteria.
- Persistent or significant incapacity or substantial disruption of the ability to conduct normal life functions
- A congenital anomaly/birth defect.
- Important medical events that may not result in death, be life-threatening, or require hospitalization may be considered a serious adverse drug experience when, based upon appropriate medical judgment, they may jeopardize the patient or subject and may require medical or surgical intervention to prevent one of the outcomes listed in this definition.

8.1.3 Life-threatening

An adverse event or suspected adverse reaction is considered "life-threatening" if, in the view of either the investigator or sponsor, its occurrence places the patient or subject at immediate risk of death. It does not include an adverse event or suspected adverse reaction that, had it occurred in a more severe form, might have caused death. (21CFR312.32)

8.1.4 Severity

The severity of each Adverse Event will be assessed utilizing the CTCAE version 5.0.

8.1.5 Relationship to Study Product

All AEs will have their relationship to study product assessed using the terms: related or not related.

- Related – There is a reasonable possibility that the study product caused the adverse event. Reasonable possibility means that there is evidence to suggest a causal relationship between the study product and the adverse event.
- Not Related – There is not a reasonable possibility that the administration of the study product caused the event.

8.2 ASSESSMENT OF SAFETY EVENTS

AE information collected will include event description, date of onset, assessment of severity and relationship to study product and alternate etiology (if not related to study product), date of resolution of the event, seriousness and outcome. The assessment of severity and relationship to the study product will be done only by those with the training and authority to make a diagnosis and listed on the Form FDA 1572 as the site principal investigator or sub-investigator. AEs occurring during the collection and reporting period will be documented appropriately regardless of relationship. AEs will be followed through resolution.

SAEs will be:

- Assessed for severity and relationship to study product and alternate etiology (if not related to study product) by a licensed study physician listed on the Form FDA 1572 as the site principal investigator or sub-investigator.
- Recorded on the appropriate SAE report form, the medical record and captured in the clinical database.
- Followed through resolution by a licensed study physician listed on the Form FDA 1572 as the site principal investigator or sub-investigator.

For timeframe of recording adverse events, please refer to section **6.1**. All serious adverse events recorded from time of the first investigational product administration must be reported to the sponsor.

8.3 REPORTING OF SERIOUS ADVERSE EVENTS

Any AE that meets protocol-defined serious criteria or meets the definition of Adverse Event of Special Interest that require expedited reporting must be submitted immediately (within 24 hours of awareness) to OSRO Safety using the CCR SAE report form.

All SAE reporting must include the elements described in section **8.2**

SAE reports will be submitted to the Center for Cancer Research (CCR) at:

[contact] and to the CCR PI and study coordinator. CCR SAE report form and instructions can be found at:

<https://ccrod.cancer.gov/confluence/display/CCRCRO/Forms+and+Instructions>

Following the assessment of the SAE by OSRO, other supporting documentation of the event may be requested by the OSRO Safety and should be provided as soon as possible.

8.4 WAIVER OF EXPEDITED REPORTING TO CCR

As death due to disease progression is part of the study objectives (PFS), and captured as an endpoint in this study, they will not be reported in expedited manner to the sponsor. However, if there is evidence suggesting a causal relationship between the study drug and the event, report the event in an expedited manner according to section [8.3](#).

8.5 SAFETY REPORTING CRITERIA TO THE PHARMACEUTICAL COLLABORATOR (BRISTOL MYERS SQUIBB)

8.5.1 Non-Serious Adverse Event Collection and Reporting

The study team will send:

Non-serious Adverse Events are to be provided to BMS in aggregate via interim or final study reports as specified in the agreement or, if a regulatory requirement [e.g. IND US trial] as part of an annual reporting requirement.

The collection of non-serious AE information should begin at initiation of study drug. All non-serious adverse events (not only those deemed to be treatment-related) should be collected continuously during the treatment period and for a minimum of 100 days following the last dose of study treatment.

Non-serious AEs should be followed to resolution or stabilization or reported as SAEs if they become serious. Follow-up is also required for non-serious AEs that cause interruption or discontinuation of study drug and for those present at the end of study treatment as appropriate.

8.5.2 Serious Adverse Event Collection and Reporting

The CCR Safety will send all reports to the manufacturer as described below:

Following the subject's written consent to participate in the study, all SAEs, whether related or not related to study drug, must be collected, including those thought to be associated with protocol-specified procedures. All SAEs must be collected that occur after the first dose of study drug and within 100 days of discontinuation of dosing.

All SAEs must be collected that relate to any protocol-specified procedure. The investigator should report any SAE that occurs after these time periods that is believed to be related to study drug or protocol-specified procedure.

SAEs, whether related or not related to study drug, and pregnancies must be reported to BMS within 24 hours of Sponsor being aware of the event. SAEs must be recorded on MedWatch form 3500a or equivalent; pregnancies on a Pregnancy Surveillance Form ([Appendix E](#)).

SAE Email Address: [contact]

SAE [contact]

If only limited information is initially available, follow-up reports are required. (Note: Follow-up SAE reports should include the same investigator term(s) initially reported.)

If any ongoing SAE changes in its intensity or relationship to study drug or if new information becomes available, a follow-up SAE report should be sent within 24 hours of Sponsor being aware of the event to the BMS (or designee) using the same procedure used for transmitting the initial SAE report.

The Sponsor will reconcile the clinical database SAE cases (case level only) transmitted to BMS Global Pharmacovigilance ([contact]). Frequency of reconciliation should be every 3 months and prior to the database lock or final data summary. BMS GPV&E will email, upon request from the Investigator, the GPV&E reconciliation report. Requests for reconciliation should be sent to [contact]. The data elements listed on the GPV&E reconciliation report will be used for case identification purposes. If the Investigator determines a case was not transmitted to BMS GPV&E, the case should be sent immediately to BMS.

All SAEs should be followed to resolution or stabilization.

8.6 REPORTING PREGNANCY

All required pregnancy reports/follow-up to OSRO will be submitted to: [contact] and to the CCR PI and study coordinator. Forms and instructions can be found here:

<https://ccrod.cancer.gov/confluence/display/CCRCRO/Forms+and+Instructions>

8.6.1 Maternal exposure

If a patient becomes pregnant during the course of the study, the study treatment should be discontinued immediately, and the pregnancy reported to the Sponsor no later than 24 hours of when the Investigator becomes aware of it. The Investigator should notify the Sponsor no later than 24 hours of when the outcome of the Pregnancy become known,

Pregnancy itself is not regarded as an SAE. However, congenital abnormalities or birth defects and spontaneous miscarriages that meet serious criteria (section **8.1.2**) should be reported as SAEs.

The outcome of all pregnancies should be followed up and documented.

8.7 REGULATORY REPORTING FOR STUDIES CONDUCTED UNDER CCR-SPONSORED IND

Following notification from the investigator, CCR, the IND sponsor, will report any suspected adverse reaction that is both serious and unexpected. CCR will report an AE as a suspected adverse reaction only if there is evidence to suggest a causal relationship between the study product and the adverse event. CCR will notify FDA and all participating investigators (i.e., all investigators to whom the sponsor is providing drug under its INDs or under any investigator's IND) in an IND safety report of potential serious risks from clinical trials or any other source, as soon as possible, in accordance to 21 CFR Part 312.32.

All serious events will be reported to the FDA at least annually in a summary format.

8.8 SPONSOR PROTOCOL DEVIATION REPORTING

A Protocol Deviation is defined as any non-compliance with the clinical trial Protocol, Manual of Operational Procedures (MOP) and other Sponsor approved study related documents. GCP or protocol-specific procedural requirements on the part of the participant, the Investigator, or the study site staff inclusive of site personnel performing procedures or providing services in support of the clinical trial.

It is the responsibility of the study Staff to document any protocol deviation identified by the Staff or the site Monitor in the CCR Protocol Deviation Tracking System (PDTs) online application. The entries into the PDTs online application should be timely, complete, and maintained per CCR PDTs user requirements.

In addition, any deviation to the protocol should be documented in the participant's source records and reported to the reviewing IRB per their guidelines. OSRO required protocol deviation reporting is consistent with E6(R2) GCP: Integrated Addendum to ICH E6(R1): 4.5 Compliance with Protocol; 5.18.3 (a), and 5.20 Noncompliance; and ICH E3 16.2.2 Protocol deviations.

9 CLINICAL MONITORING PLAN

Clinical site monitoring is conducted to ensure:

- that the rights of the participants are protected;
- that the study is implemented per the approved protocol, Good Clinical Practice and standard operating procedures; and,
- the quality and integrity of study data and data collection methods are maintained.

Monitoring for this study will be performed by NCI CCR Office of Sponsor and Regulatory Oversight (OSRO) Sponsor and Regulatory Oversight Support (SROS) Services contractor. Clinical site monitoring activities will be based on OSRO standards, FDA Guidance E6(R2) Good Clinical Practice: Integrated Addendum to ICH E6(R1) March 2018, and applicable regulatory requirements.

Details of clinical site monitoring will be documented in a Clinical Monitoring Plan (CMP) developed by OSRO. CMPs will be protocol-specific, risk-based and tailored to address human subject protections and integrity of the study data. OSRO will determine the intensity and frequency of monitoring based on several factors, including study type, phase, risk, complexity, expected enrollment rate, and any unique attributes of the study and the site. The Sponsor will conduct a periodic review of the CMP to confirm the plan's continued appropriateness. A change to the protocol, significant or pervasive non-compliance with GCP, or the protocol may trigger CMP updates.

OSRO SROS Monitoring visits and related activities will be conducted throughout the life cycle of each protocol. The first activity is before the study starts to conduct a Site Assessment Visit (SAV) (as warranted), followed by a Site Initiation Visit (SIV), Interim Monitoring Visit(s) (IMVs), and a study Close-Out Visit (COV).

Some monitoring activities may be performed remotely, while others will occur at the study site(s). Monitoring visit reports will describe visit activities, observations, and associated action items or follow-up required for resolution of any issues, discrepancies, or deviations. Monitoring reports will be distributed to the study PI, NCI CCR QA, CCR Protocol Support Office, coordinating center (if applicable), and the Sponsor regulatory file.

The site Monitor will inform the study team of any deviations observed during monitoring visits. If unresolved, the Monitor will request that the site Staff enter the deviations in the CCR Protocol Deviation Tracking System (PDTs) for deviation reporting to the Sponsor and as applicable per institutional and IRB guidance.

10 STATISTICAL CONSIDERATIONS

10.1 STATISTICAL HYPOTHESIS

10.1.1 Primary Endpoint: PFS at 6 months

Hypothesis: The PFS6 for HMP cohort is 30% or better, and PFS6 for NHMP is 39% or better.

Simon's optimal two-stage design [57] will be used for conducting the trial for the HMP and NHMP cohorts independently. Specifically, for the HMP cohort, the null hypothesis is that the PFS6 is 0.1, and the alternative hypothesis is that the PFS6 is 0.3. The trial is carried out in two stages. In stage I, a total number of 10 patients is accrued. If 9 or more patients progressed by 6 months, the cohort will be terminated early; otherwise, additional 19 patients will be accrued in stage II, resulting in a total sample size of 29. Among these 29 patients, if 6 or more patients are progression-free at 6 months, we reject the null hypothesis and claim that the treatment is promising for patients with HMP IDH-mutant gliomas. The design controls the type I error rate at 0.05 and yields the power of 0.8.

For the NHMP cohort, the null hypothesis is that the PFS6 is 0.186, and the alternative hypothesis is that the PFS6 is 0.386. The trial is carried out in two stages. In stage I, a total number of 15 patients is accrued. If 3 or more patients are progression-free at 6 months, the cohort will be moved to stage II and additional 15 patients will be accrued in stage II, resulting in a total sample size of 30. Among these 30 patients, if 10 or more patients are progression-free at 6 months, we reject the null hypothesis and claim that the treatment is promising for patients with NHMP IDH-mutant gliomas. The design controls the type I error rate at 0.05 and yields the power of 0.8.

Rationale for the target PFS6 in HMP and NHMP cohorts:

Due to the rarity of the disease, there is lack of large scale of studies to provide the accurate survival data of this subset of patients. Based on our anecdotal experience, the HMP IDH-mutant recurrent gliomas have similar course of disease progression as recurrent glioblastoma, while the NHMP ones have similar course as recurrent anaplastic astrocytoma. Wong et al. reported that a progression free survival rate at 6 months (PFS6) is 31% and the median progression free survival is only 13 weeks based on eight Phase II clinical trials that included 150 patients with recurrent anaplastic astrocytoma[58, 59]. In the pivotal clinical trial that led to the accelerated FDA approval for TMZ as the treatment of recurrent AA, the PFS6 and median overall survival were reported as 46% and 13.6 months respectively[59]. Based on these, we set the PFS targets (P0=30% and P1=50%) for NHMP. In the same study, the PFS at 6 for GBM is 15% and median PFS is 9 weeks. Therefore, we used 10% as P0 for HMP gliomas in this proposed study.

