- A Simon's optimal two-stage design will be used to conduct the HMP arm and the NHMP arm independently. For the HMP cohort, in stage I, a total number of 10 patients are accrued. If 9 or more patients progress by 6 months, the cohort will be terminated early; otherwise, additional 19 patients will be accrued in stage II, resulting in a total sample size of 29. Among these 29 patients, if 6 or more patients are progression-free at 6 months, we will claim that the treatment is promising for patients with HMP IDH-mutant gliomas. For NHMP cohort, in stage I, a total number of 15 patients are accrued. If 3 or more patients are progression-free at 6 months, the cohort will move to stage II and additional 15 patients will be accrued in stage II, resulting in a total sample size of 30. Among these 30 patients, if 10 or more patients are progression-free at 6 months, we will claim that the treatment is promising for patients with NHMP IDH-mutant gliomas.

TABLE OF CONTENTS

PRÉCIS.....	2
TABLE OF CONTENTS	4
STATEMENT OF COMPLIANCE	10
1 INTRODUCTION	11
1.1 Study Objectives	11
1.1.1 Primary Objective	11
1.1.2 Secondary Objectives	11
1.1.3 Exploratory Objectives	11
1.2 Background and Rationale.....	11
1.2.1 IDH mutation dictates glioma biology	11
1.2.2 IDH-mutant gliomas accumulate increased mutation burden during higher grade transformation.....	12
1.2.3 Cancers with high mutation burden better respond to checkpoint inhibitors	12
1.2.4 Nivolumab is used as an immune therapy for gliomas.....	13
1.2.5 Rationale for the patient-reported outcome studies	14
1.2.6 Rationale for the correlative studies with biospecimen.....	15
1.2.7 Rationale for changing sample number of NHMP cohort	15
2 ELIGIBILITY ASSESSMENT AND ENROLLMENT	16
2.1 Eligibility Criteria	16
2.1.1 Inclusion Criteria	16
2.1.2 Exclusion Criteria	17
2.1.3 Recruitment Strategies.....	18
2.2 Screening Evaluation	18
2.2.1 Screening activities performed prior to obtaining informed consent	18
2.2.2 Screening activities performed after a consent for screening has been signed.....	18
2.3 Participant Registration and Status Update Procedures.....	19
2.3.1 Screen Failures.....	19
2.3.2 Treatment Assignment Procedures (For registration purposes only):	19
2.4 Baseline Evaluation.....	20
3 STUDY IMPLEMENTATION	20

3.1	Study Design	20
3.2	Drug Administration	21
3.3	Dose Modifications	21
3.4	Questionnaires.....	27
3.5	Study Calendar.....	28
3.6	Cost and Compensation	32
3.6.1	Costs	32
3.6.2	Compensation	32

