1.2.7 Rationale for changing sample number of NHMP cohort

Under the protocol version C (version date 12/09/2021), we performed an interim analysis after a total number of 15 NHMP patients were accrued. 6 patients are progression-free at 6 months. Per protocol, NHMP cohort should proceed to stage II and recruit additional 31 patients. When the characteristics of the 15 patients treated in this cohort were analyzed, 8 of the 15 patients had diagnosis of glioblastoma (WHO grade 4) prior to the study treatments, 6 with anaplastic glioma

(WHO grade 3) and only one with grade II glioma. The distribution of the tumor histology for this cohort was unexpected. The original sample size calculation of the current protocol was based on the expectation of grade III gliomas being the predominant histology, which led to setting the null hypothesis PFS6 being 0.3 (usually used for grade 3 gliomas) and the alternative hypothesis PFS6 being 0.5. As a result, the two-stage design required 6 or more patients among 15 treated patients achieve PFS6 to move to stage II, where additional 31 patients will be enrolled.

In light of the unexpected patient population that were treated in the NHMP cohort, the null and alternative hypotheses, as well as the two-stage design, should be adjusted to reflect the actual patient population. Based on the literature, PFS6 is 0.3 for grade 3 gliomas, and 0.1 for grade 4 glioblastoma. Thus, the updated null hypothesis for PFS6 = $(0.1 \times 8 + 0.3 \times 6) / (8 + 6) = 0.186$. Assuming 20% improvement as the original design, the alternative hypothesis for PFS6 is 0.386. Employing the Bayesian optimal phase 2 design, the updated 2-stage design becomes: enroll 15 patients, if there are 3 or more patients are progression-free at 6 months, move to stage II and enroll additional 15 patients. Among the total of 30 patients, if 10 or more patients are progression-free at 6 months, we claim that the treatment is promising for patients with NHMP IDH-mutant gliomas. This updated design yields 77.5% power, while controlling one-sided alpha at 0.05.

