10.1.1.1 Sample Size Determination

A maximum of 29 patients with HMP IDH-mutant gliomas, and a maximum of 30 patients with NHMP IDH-mutant gliomas will be enrolled in this phase II trials. Under the design described previously and given the type I error rate of 0.05, we have 80% power to reject the null hypothesis PFS6 = 0.1 for the HMP cohort given the alternative hypothesis PFS6 = 0.3; and 80% power to reject the null hypothesis PFS6 = 0.19 for the NHMP cohort given the alternative hypothesis PFS6 = 0.39.

Up to 59 study patients who undergo at least 1 cycle (2 infusions of nivolumab) is required. As we take into account approximately 20% of screen failures/non-evaluable patients, the overall accrual ceiling is 70 study patients.

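### Sections 10.1.1 and 10.1.1.1 give the NHMP rule 80% power and 10.1.1 labels it Simon's optimal; its exact power is 77.5%, and section 1.2.7 calls it a Bayesian optimal phase 2 design

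*Combined protocol and SAP*

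**What the plan says.** Section 10.1.1 places both cohorts under one method: "Simon's optimal two-stage design [57] will be used for conducting the trial for the HMP and NHMP cohorts independently". The Précis does the same: "A Simon's optimal two-stage design will be used to conduct the HMP arm and the NHMP arm independently". For NHMP, section 10.1.1 sets a null PFS6 of 0.186 and an alternative of 0.386. Stage I has 15 patients, and 3 or more progression-free at 6 months opens stage II. A further 15 are then enrolled, and 10 or more of the 30 counts as success. The paragraph ends: "patients with NHMP IDH-mutant gliomas. The design controls the type I error rate at 0.05 and yields the power of 0.8".

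Section 10.1.1.1 rounds the rates to 0.19 and 0.39 and claims "80% power to reject the null hypothesis PFS6 = 0.19 for the NHMP cohort".

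Section 1.2.7 explains where the current rule came from. It gives the same hypotheses and cut-offs, but a different method, "Employing the Bayesian optimal phase 2 design, the updated 2-stage design becomes", and a different power: "This updated design yields 77.5% power, while controlling one-sided alpha at 0.05". It also describes the design that was replaced, with rates 0.3 and 0.5, which "required 6 or more patients among 15 treated patients achieve PFS6 to move to stage II, where additional 31 patients will be enrolled".

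**The concern.** The document gives two powers and two design names for one decision rule on a primary hypothesis. The statistical section, which readers will cite, carries the higher power and the Simon name. If the exact power is 77.5%, section 10 understates the type II error (22.5% rather than 20%). It also names and references a method that section 1.2.7 says was not the one used. Anyone who tries to regenerate the NHMP design from the method and inputs in section 10.1.1 would then arrive at different cut-offs and a different sample size.

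**Working it through.** **Inputs** (section 10.1.1): n1 = 15, continue if X1 ≥ 3; n = 30, succeed if X1 + X2 ≥ 10; p0 = 0.186, p1 = 0.386. Section 10.1.1.1 gives the rounded pair 0.19 and 0.39.

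**Formula.** The probability of declaring success at true rate p is

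S(p) = Σ over x = 3,…,15 of Bin(x; 15, p) × P(Bin(15, p) ≥ 10 − x).

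**Control on the HMP rule.** The same calculation for at least 2 of 10, then at least 6 of 29, gives 0.0471 at 0.1 and 0.8051 at 0.3. Both agree with section 10.1.1, so the method reproduces the plan's HMP figures.

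**NHMP rule.**

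| True PFS6 | S(p) | Role | Plan states |
|---|---|---|---|
| 0.186 | 0.0389 | type I error | at most 0.05 |
| 0.386 | 0.7748 | power | 0.8 (10.1.1); 77.5% (1.2.7) |
| 0.19 | 0.0443 | type I error | at most 0.05 |
| 0.39 | 0.7879 | power | 80% (10.1.1.1) |

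The 77.5% in section 1.2.7 reproduces; the 80% does not. The shortfalls are 80 − 77.5 = 2.5 points and 80 − 78.8 = 1.2 points.

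**Could another reading of the rule give 80%?**
- With no stage I stop, P(Bin(30, 0.386) ≥ 10) = 0.7803. An early stop for futility can only lower this, so no stage I rule reaches 80% at 0.386 with a final cut-off of 10 of 30.
- A final cut-off of 9 of 30 gives power 0.866 but type I error 0.087.
- A final cut-off of 11 of 30 gives power 0.650.
- Rates of 0.20 and 0.40 give power 0.819 but type I error 0.060.

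**Is the rule Simon's optimal?** That design minimises the expected sample size under the null, subject to the error limits. The stated rule stops early at 0.186 with probability P(Bin(15, 0.186) ≤ 2) = 0.452, so its expected size is 15 + 15 × (1 − 0.452) = 23.2. An exhaustive search with type I error at most 0.05 and power at least 0.80 gives:

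| Rates | Simon optimal | Type I error | Power | Expected N under null |
|---|---|---|---|---|
| 0.186 / 0.386 | ≥4/14, then ≥12/40 | 0.0411 | 0.8033 | 20.6 |
| 0.19 / 0.39 | ≥4/14, then ≥12/39 | 0.0410 | 0.8017 | 20.7 |
| 0.3 / 0.5 (superseded NHMP rates) | ≥6/15, then ≥19/46 | 0.0499 | 0.8032 | 23.6 |
| 0.1 / 0.3 (HMP) | ≥2/10, then ≥6/29 | 0.0471 | 0.8051 | – |

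The stated NHMP rule matches neither of the first two rows. Lowering the power target to 77.5% does not help: the optimum is then ≥4/14, ≥10/32, with expected size 18.6.

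**Likely origin.** The third row matches the replaced design in section 1.2.7: 6 of 15, and 15 + 31 = 46 patients. The final cut-off of 19 comes from the search; the documents do not give it. The Simon label and the power of 0.8 were thus correct for that design. The rationale paragraph in section 10.1.1 also still gives 30% and 50% as the NHMP targets.

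**The case against.** The strongest reply is that the numerical gap is small. Section 10.1.1 prints one decimal, and 0.7748 rounds to 0.8. Section 10.1.1.1 does print 80%, but at rates where the exact figure is 78.8%, a gap of 1.2 points. The correct power and method are already in section 1.2.7, so nothing is withheld. No cut-off, sample size or analysis depends on the correction. The expected-size comparison is secondary, because section 1.2.7 does not claim that the rule minimises expected size.

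Much of this stands as a limit on weight. One-decimal rounding can cover section 10.1.1 taken alone. It cannot cover the 80% in section 10.1.1.1, nor the conflict with the 77.5% in section 1.2.7. The expected sizes serve only to show that the Simon label does not fit; they are not a criticism of the rule's efficiency. That the wording was left over from the replaced design is an inference, and the correction does not depend on it. Section 1.2.7 derives the rule now in force, so this is not a difference between current text and a record of superseded text.

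**Conclusion.** The point holds. At 0.186 against 0.386 the NHMP rule has power 77.5%, not 80%, and at the rounded 0.19 against 0.39 it has 78.8%. The Simon label is wrong for this cohort and contradicts section 1.2.7. The statement on type I error is sound as a nominal figure (0.039 at 0.186, 0.044 at 0.19). The HMP label and figures are correct. The NHMP cut-offs are the same in the Précis and in sections 1.2.7, 3.1, 10.1.1 and 10.3.4 wherever each is given, so the defect is confined to a power figure and a design name.

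These results assume independent binary outcomes, all 30 patients evaluable at 6 months, and a rule fixed in advance. The last assumption does not describe what happened: section 1.2.7 reports that the stage I result was known when the rule was changed ("6 patients are progression-free at 6 months. Per protocol, NHMP cohort should proceed to stage II and recruit additional 31 patients"). The values 0.039 and 77.5% are therefore nominal. The correction should be made, because the error concerns a primary hypothesis and costs almost nothing to put right.

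**What to change.** 1. In section 10.1.1, give the NHMP power as 77.5% at 0.186 against 0.386.
2. In section 10.1.1.1, give the same figure and replace the rounded 0.19 and 0.39 with 0.186 and 0.386, so that rates and power belong together.
3. In the Précis and section 10.1.1, limit the Simon label and its reference to the HMP cohort, and name the NHMP design as section 1.2.7 does.
4. Add one sentence stating that the NHMP error rates (type I 0.039, power 77.5%) are nominal values for a rule fixed in advance, and that the rule was revised after 6 of 15 stage I patients were known to be progression-free.

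The cost is wording only, in three places. Cut-offs, sample size and analysis do not change.
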